### 5.7.2. Analysis of Clinical Laboratory Measurements

Laboratory measurements include clinical chemistry, hematology and urinalysis results, and will be converted to standard international units and US conventional units. Summaries of laboratory variables will include:

- Descriptive statistics of laboratory result and change from baseline by visit

- The number (n) and percentage (%) of subjects with treatment emergent PCSVs. This summary will be provided based on all patients in the SAF as well as in the subgroup of SAF patients who did not meet the PCSV criterion at baseline.
- Shift tables based on baseline normal/abnormal and other tabular and graphical methods may be used to present the results for parameters of interest

### **5.7.3. Analysis of Vital Signs**

Summaries of vital sign variables will include:

- Descriptive statistics of vital sign variable and change from baseline by visit
- The number (n) and percentage (%) of patients with treatment-emergent PCSV
- Shift tables based on baseline normal/abnormal and other tabular and graphical methods may be used to present the results for parameters of interest

### **5.7.4. Analysis of 12-Lead ECG**

Summaries of 12-lead ECG parameters by treatment group will include:

- Each ECG parameter and change from baseline
- The number (n) and percentage (%) of subjects with PCSV, depending on data
- ECG status (i.e. normal, abnormal) summarized by a shift table

### **5.7.5. Analysis of Physical Exams**

The number (n) and percentage (%) of patients with abnormal physical exams will be summarized at baseline, end of treatment period and end of study by treatment group. Shift table for physical exams status will be provided. A summary of treatment-emergent abnormal findings will be provided, as appropriate.

## **5.8. Analysis of Pharmacokinetic Data**

The following analyses will be conducted:

- Descriptive statistics of functional dupilumab concentrations in serum at each sampling time by dose
- Graphical presentations of median and mean (+/- SD) functional dupilumab concentration in serum vs nominal time profiles
- Graphical presentations of individual functional dupilumab concentration in serum vs actual sampling time profiles
- Assessment of the impact of anti-drug antibodies on functional dupilumab concentrations in serum.

No formal statistical analysis will be performed.

## **5.9. Analysis of Immunogenicity Data**

### **5.9.1. Analysis of ADA Data**

The immunogenicity variables described in Section 4.7 will be summarized using descriptive statistics in the ADA analysis set.

Immunogenicity will be characterized by ADA responses and titers observed in patients in the ADA analysis set.

The following will be summarized by treatment group and ADA titer level:

- Number (n) and percent (%) of ADA-negative subjects
  - Number (n) and percent (%) of pre-existing immunoreactivity subjects
- Number (n) and percent (%) of treatment-emergent ADA-positive patients
  - Number (n) and percent (%) of persistent treatment-emergent ADA positive patients
  - Number (n) and percent (%) of indeterminate treatment-emergent ADA positive patients
  - Number (n) and percent (%) of transient treatment-emergent ADA positive patients
- Number (n) and percent (%) of treatment-boostered ADA-positive patients

Listing of all ADA titer levels will be provided for patients with pre-existing, treatment-emergent and treatment-boostered ADA response.

### **5.9.2. Analysis of Neutralizing Antibodies (NAb)**

Samples positive in the ADA assay will be further characterized for the presence of neutralizing antibodies (NAb) for dupilumab. The absolute occurrence (n) and percent of patients (%) with NAb status (positive or negative) will be provided for patients in the NAb analysis set.

## **5.10. Association of Immunogenicity with Exposure, Safety and Efficacy**

### **5.10.1. Association of immunogenicity with exposure**

Potential association between immunogenicity variables and systemic exposure to dupilumab will be explored by treatment groups. Plots of dupilumab concentration may be provided for analyzing the potential impact of treatment-emergent, persistent ADA response and titer (high, moderate or low) and NAb on PK profiles.

### **5.10.2. Immunogenicity and Safety/ Efficacy**

Potential association between immunogenicity variables and safety events will focus on the following events:

- Injection site reaction (serious or severe and lasting 24 hours or longer)
- Hypersensitivity (SMQ: Hypersensitivity [Narrow])

- Anaphylactic Reaction (SMQ: Anaphylactic Reaction [Narrow])

Potential association between immunogenicity variables and the co-primary efficacy endpoints may be explored (e.g. scatter plot or spaghetti plot).

The safety and efficacy analyses mentioned above will be conducted using the following ADA response categories:

- ADA positive patients, that is patients with treatment-emergent or treatment-boosted response
- ADA negative patients, that is patients with pre-existing immunoreactivity or negative in the ADA assay at all time points
- Patients with persistent ADA response
- NAb positive patients, that is patients who were positive in the NAb assay at any time point analyzed.
- Maximum post-baseline titer level in treatment-emergent or treatment-boosted ADA positive patients:  
Low (titer <1,000), Moderate ( $1,000 \leq \text{titer} \leq 10,000$ ), and High (titer >10,000)

### 5.11. Analysis of Biomarker Data

Descriptive statistics for the observed values, change from baseline and percent change from baseline values by treatment and visit will be provided for the following biomarker variables:

- TARC
- total serum IgE
- Serum Immunoglobulin profile (IgG/IgM/IgA)
- Lactate dehydrogenase (LDH)

The Wilcoxon signed-rank test will be used to test if the change or percentage change from baseline value is significantly different from zero. P-value will be reported.

Exploratory analyses for the difference between dupilumab groups and placebo of the change from baseline and percent change from baseline values will be performed using a rank-based ANCOVA model with treatment group as a fixed effect, and the relevant baseline values as covariate. Missing values will be imputed by LOCF method for visits between post-baseline and week 16. After week 16, no imputation will be made. P-value for difference from placebo will be provided.

Relationship of baseline TARC and baseline IgE with the following clinical endpoints will be explored using ANCOVA model. The model includes the below clinical endpoint as the dependent variable and the log10 based transformed baseline biomarker data, treatment group and their interaction as the predictor variables. Model coefficients and P-value will be provided.

- Percent change from baseline to week 16 in EASI score
- Percent change from baseline to week 16 in weekly average of daily worst scratch/itch NRS score

- Change from baseline to week 16 in percent BSA affected by AD
- Percent change from baseline to week 16 in SCORAD

Relationship of baseline TARC and baseline IgE with the following clinical endpoints will be explored using the logistic model. The model includes the responder/non-responder of the below clinical endpoints as the dependent variable and the log10 based transformed baseline biomarker data, treatment group and their interaction as the predictor variables. Model coefficients and P-value will be provided to indicate significance of the correlation/association.

- IGA 0-1 at week 16
- EASI-75 at week 16
- Improvement (reduction) of weekly average of worst scratch/itch scale  $\geq 4$  from baseline to week 16

Association of positivity to at least one antigen-specific IgE with the following clinical endpoints may be explored using CMH test stratified by randomization strata. The risk ratio and P-value will be provided.

- IGA 0-1 at week 16
- EASI-75 at week 16
- improvement (reduction) of weekly average of worst scratch/itch scale  $\geq 4$  from baseline to week 16

All above analyses will be performed on the FAS for

- All observed data, regardless if rescue treatment is used or data is collected after study drug withdrawal
- All observed data with censoring after rescue treatment use

The proportion of patients for whom biomarker concentrations “normalize” (shift from above normal to within the normal range) at Week 16 will also be evaluated.

The additional analysis will be performed on the following biomarkers at week 16:

- Serum total IgE
- Serum LDH

Serum total IgE and LDH have established clinical assays; the upper limit of normal (ULN) from the central lab reference range will determine the threshold for normal vs. elevated status.

Summary tables with normal/elevated status for serum total IgE and LDH at baseline and each post-baseline visit (until end-of-study) will be provided by treatment group.

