9.1. Statistical Hypothesis

Part A of the study is open-label; therefore, no statistical hypotheses will be tested in this portion of the study.

For part B of the study, the following null hypothesis and alternative will be tested for the dupilumab treatment group:

H0: There is no treatment difference between dupilumab and placebo

H1: There is a treatment difference between dupilumab and placebo

Baseline weight group, baseline disease severity (IGA=3, 4), and region/country will be the 3 stratification factors for patient randomization that will be accounted for in the statistical modeling for efficacy.

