9.5.6. Analysis of Biomarker Data

In parts A and B, all exploratory biomarker data analyses will be performed on the SAF and no multiplicity adjustment is planned. Analyses of blood biomarker endpoints (TARC and IgE) will be provided in the SAP and results will be presented in the final clinical study report. Analyses from tape stripping and genomics sub-studies will not be reported in the clinical study report.

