**Figure 1: Overall Design**

The Part A of AD-1539 has been completed. The CSR has been finalized and approved in Dec 2020. This document focuses on Part B of the study only.

AD-1539 B is a randomized, double-blind, placebo-controlled, parallel-group study to investigate the efficacy and safety of SC dupilumab when administered concomitantly with TCS in pediatric patients,  $\geq 6$  months to  $< 6$  years of age, with moderate-to-severe AD. Approximately 160 patients are planned to be randomized in the study. The number of patients with moderate AD (IGA=3) is capped at approximately 40 patients. Figure 1 shows the overall design of AD-1539 (Parts A and B).

[figure not shown]
Part B consists of the following 3 periods: a screening period of up to 56 days (including 2 weeks of TCS standardization), a treatment period of 16 weeks, and a follow-up period of 12 weeks (Figure 3). Patients who enrolled in Part A of the study are not eligible to participate in Part B.

Patients who continue to meet eligibility criteria at baseline undergo day 1/baseline assessments. Patients are randomized in a 1:1 ratio stratified by baseline body weight ( $\geq 5$ - $< 15$  kg and  $\geq 15$ - $< 30$  kg), baseline disease severity (IGA=3 and 4), and region/country (North America and Europe). Approximately 160 patients are randomized to 1 of the following 2 treatment regimens (Figure 2):

- dupilumab Q4W tiered fixed-dose (200 mg or 300 mg) treatment regimen:
  - Patients with baseline weight  $\geq 5$  to  $< 15$  kg receive an SC injection of 200 mg dupilumab (1.14 mL of a 175 mg/mL solution) on day 1 and then 200 mg Q4W from week 4 to week 12.
  - Patients with baseline weight  $\geq 15$  to  $< 30$  kg receive an SC injection of 300 mg dupilumab (2 mL of a 150 mg/mL solution) on day 1 and then 300 mg Q4W from week 4 to week 12.
- placebo Q4W treatment regimen: patients receive matching placebo on day 1 and then Q4W from week 4 to week 12.
  - In the  $\geq 5$  to  $< 15$  kg weight stratum, patients randomized to placebo receive Q4W injections of placebo (1.14 mL) matching 200 mg dupilumab.

- In the  $\geq 15$  to  $< 30$  kg weight stratum, patients randomized to the placebo group receive Q4W SC injections of placebo (2 mL) matching 300 mg dupilumab.

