### 5.6.1. Analysis of Primary/Co-Primary Efficacy Variable

The Cochran-Mantel-Haenszel (CMH) test adjusted by randomization strata (baseline weight group:  $\geq 5$ - $<15$  kg and  $\geq 15$ - $<30$  kg), baseline disease severity (IGA=3 and 4), and region/country (North America, Europe)) will be used for the analysis of percentage of patients with IGA 0 or 1 at week 16. Similar procedures will be used for percentage of patients with EASI-75 at week 16. At the time of this SAP, all patients for this study have been randomized. The smallest stratum (region = EU, baseline weight  $<15$  kg, IGA=3) has 2 subjects only. All other strata have more than 10 patients. In all statistical analysis utilizing stratification factors in CMH test, stratum (region = EU, baseline weight  $<15$  kg, IGA=3) will be combined with the stratum (region = EU, baseline weight  $\geq 15$  kg, IGA=3).

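### The between-arm biomarker rank ANCOVA in SAP 5.11 leaves out the three randomisation strata, which makes an exploratory comparison mildly conservative if those strata are prognostic

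*SAP*

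**What the plan says.** SAP 2.1 sets the allocation: "Patients are randomized in a 1:1 ratio stratified by baseline body weight", together with baseline IGA (3 or 4) and region (North America or Europe).

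For the biomarkers, SAP 5.11 plans "Exploratory analyses for the difference between dupilumab groups and placebo of the change from baseline and percent change from baseline values", to be fitted with a "rank-based ANCOVA model with treatment group as a fixed effect, and the relevant baseline values as covariate". Weight group, IGA and region are not in that model.

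The strata do appear elsewhere in the SAP:
- the CMH test for the primary and co-primary endpoints (5.6.1);
- the ANCOVA for continuous secondary endpoints (5.6.2);
- the Cox model for time to first adverse event of special interest (5.7.1);
- within 5.11, the association of antigen-specific IgE with response, which "may be explored using CMH test stratified by randomization strata".

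Protocol 9.1 says the three factors "will be the 3 stratification factors for patient randomization that will be accounted for in the statistical modeling for efficacy". Protocol 9.5.6 classes the biomarker analyses as exploratory, without multiplicity adjustment.

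**The concern.** Stratified randomisation balances the arms on weight group, IGA and region. That balance takes the between-stratum component out of the true variance of the treatment difference. A model without the strata leaves the same component in its residual, so it reports a standard error larger than the real one. The test remains valid but gives away some power.

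The strata could well matter for these markers. Protocol 6.2.5 links TARC and LDH to disease severity, and IGA is a severity factor. Weight follows age: Protocol 1.2.2 gives Part A mean weights of 17.1 kg at 2 to <6 years and 9.8 kg at 6 months to <2 years. What counts is how much the strata explain after the baseline biomarker is in the model, and the documents do not say.

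At stake is the sharpness of one exploratory comparison. The effect on blood biomarkers against placebo is listed for Part B under Other Objectives (Protocol 2.3).

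**Working it through.** **Plan's own figures.** The documents give no power, SD or R² for any biomarker analysis. The one relevant planning figure that can be checked is the sample size of 80 per group, with 88% power for IGA 0/1 at 32.8% versus 11.4% (SAP 2.3). Exact enumeration of the two-sided Fisher test gives 88.9%, which reproduces it. I therefore use N = 160.

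**Inputs.**
- N = 160, 80 per arm, allocated 1:1 (SAP 2.1, 2.3).
- Strata main effects: weight 1 df, IGA 1 df, region 1 df (two regions in SAP 5.6.1), 3 df in all.
- R², the share of residual outcome variance that the strata explain beyond the baseline biomarker: assumed, 0 to 0.20.
- Treatment effect: assumed 0.443 SD, chosen to give 80% power without strata. Check: 0.443/√(2/80) = 2.80, and Φ(2.80 − 1.96) = 0.80.

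**Formulas.**
- SE ratio (with strata / without) = √(1 − R²).
- Equivalent extra patients = 1/(1 − R²) − 1.
- Power = Φ(2.80/SE ratio − 1.96).
- Charge for three extra parameters: multiply the variance by (160 − 5)/(160 − 8) = 155/152. Break-even is at R² = 1 − 152/155 ≈ 0.02.

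| Assumed R² | SE ratio | Equivalent extra patients | Power with strata | Power after charge |
|---|---|---|---|---|
| 0 | 1.000 | 0% | 80% | 79% |
| 0.05 | 0.975 | 5% | 82% | 81% |
| 0.10 | 0.949 | 11% | 84% | 83% |
| 0.20 | 0.894 | 25% | 88% | 87% |

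**Simulation of the rank ANCOVA.** N = 160; stratified blocks of 4; 75% with IGA 4, which matches a cap of about 40 with IGA 3 out of 160; weight split 50/50 and region 35/65 (both assumed); 4,000 runs per setting.

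| Assumed R² | Power without strata | Power with strata | Null rejection without | Null rejection with |
|---|---|---|---|---|
| 0 | 77.7% | 77.5% | 4.9% | 4.9% |
| 0.05 | 77.5% | 78.5% | 4.3% | 4.6% |
| 0.10 | 77.1% | 80.3% | 4.4% | 5.4% |
| 0.20 | 79.5% | 85.3% | 3.4% | 5.1% |

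The Monte Carlo error on a 5% rejection rate is √(0.05 × 0.95/4000) ≈ 0.34 points. The 3.4% is therefore clearly below 5%, while 5.4% is within noise.

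Theory agrees. With perfect balance the unadjusted test rejects a true null with probability 2Φ(−1.96/√(1 − R²)), which is 3.9% at R² = 0.10 and 2.8% at 0.20. Incomplete blocks bring the simulated values closer to 5%.

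The simulated cost of adding the strata when they explain nothing is 0.2 points, less than the formula's charge of about 1 point. Stratified allocation has already removed most of the chance imbalance that the charge allows for.

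**Feasibility.** SAP 5.6.1 reports one cell of 2 patients (Europe, <15 kg, IGA 3) and says "All other strata have more than 10 patients". Main effects pool across cells, so the small cell does not prevent fitting.

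**The case against.** The strongest reply is that this is a matter of preference in an analysis that decides nothing. It is labelled exploratory, is not in the testing hierarchy of SAP 5.6.3, and Protocol 9.1 ties stratum adjustment to efficacy. The baseline biomarker is already a covariate and may absorb much of what IGA and weight would explain, leaving R² near zero and no gain. All of that stands as a limit on size and importance. It is not a reason to leave the strata out, because the loss when they are useless is negligible.

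A reader might infer three stronger points, none of which the documents support.

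- *A protocol breach.* The commitment in Protocol 9.1 covers efficacy modelling only.
- *An invalid test.* Omission lowered the rejection rate under the null; it did not inflate it.
- *The same precision loss in the biomarker-response models of SAP 5.11*, which use log10 baseline biomarker, "treatment group and their interaction as the predictor variables". For the logistic models, adjustment does not shrink the standard error of a log odds ratio; it moves the target to a conditional one. In simulation (1,500 runs per setting) the treatment SE rose from 0.453 to 0.458, 0.442 to 0.456 and 0.422 to 0.458 as stratum effects grew. Interaction power was flat (14.3% and 13.7%, 15.0% and 15.1%, 14.9% and 14.5%, without and with strata). The extra terms also have a price: at planning rates about 80 × 0.328 + 80 × 0.114 ≈ 35 IGA responders are expected, so three predictors become six and events per predictor fall from about 12 to about 6. For both the ANCOVA and the logistic versions, baseline TARC and IgE are not randomised. Adjusting for severity changes the question from a marker's overall relation with response to its value beyond severity. Either question is defensible.

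**Conclusion.** The point holds for the between-arm rank ANCOVA only. That model omits factors which the trial randomised by and which the SAP uses in its other main comparative models and once in the same section, without explanation. If the strata are prognostic beyond baseline, the test is mildly conservative: null rejection falls to 3.4% at R² = 0.20. Adding the strata then gains between nothing and about 6 to 8 power points over R² from 0 to 0.20 (5.8 in simulation, 7 to 8 by formula at the top of the range).

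The size rests on an R² that the documents do not supply, so a specific gain should not be claimed. It also rests on about 160 patients contributing. This is a low-priority improvement with no effect on any primary, key secondary or sample-size result.

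**What to change.** In SAP 5.11, add baseline weight group, baseline IGA (3 or 4) and region as main effects to the rank-based ANCOVA for change and percent change in each biomarker. Apply this in both planned data sets, with and without censoring after rescue. Specify main effects rather than the full cross-classification, so that the 2-patient cell needs no special handling.

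Leave the ANCOVA and logistic biomarker-response models as written.

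The cost is one sentence of SAP text and 3 degrees of freedom out of about 160. The factors are already in the data for the efficacy analyses, so nothing new need be collected.

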2.3. Other Objectives

[figure not shown]
The other objectives of part B of the study is:

- To assess the concentrations of dupilumab in serum following repeated SC dosing.
- To assess the effects of dupilumab on blood and skin biomarkers of inflammation in comparison with placebo.
- To study dupilumab's mechanism of action (related to efficacy and/or safety), why some patients respond better than others (safety and/or efficacy), type 2 inflammation, as well as AD and related diseases.

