#### 3.1. The Full Analysis Set (FAS)

The full analysis set (FAS) includes all randomized patients. Efficacy analyses will be based on the treatment allocated at randomization (as randomized). All efficacy variables will be evaluated in the FAS, which will be the primary analysis set.

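### The antigen-specific IgE analysis names no treatment term, so its single risk ratio cannot separate a marker of dupilumab response from a prognostic one

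*SAP*

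**What the plan says.** **Method and output.** SAP 5.11: "Association of positivity to at least one antigen-specific IgE with the following clinical endpoints may be explored using CMH test stratified by randomization strata". The endpoints are IGA 0/1, EASI-75 and an itch reduction of at least 4 points, all at week 16. On output it says: "The risk ratio and P-value will be provided".

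**Strata.** Protocol 9.1: "Baseline weight group, baseline disease severity (IGA=3, 4), and region/country will be the 3 stratification factors for patient randomization". SAP 5.6.1 uses the same three. Treatment is not one of them.

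**Analysis set.** SAP 5.11: "All above analyses will be performed on the FAS for" observed data, with and without censoring at rescue. SAP 3.1: "The full analysis set (FAS) includes all randomized patients". Protocol 9.5.6 differs: "all exploratory biomarker data analyses will be performed on the SAF and no multiplicity adjustment is planned". Either set contains both arms.

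**Neighbouring models.** For the same three endpoints, SAP 5.11 relates baseline TARC and baseline IgE to response by logistic regression with the log-transformed biomarker, "treatment group and their interaction as the predictor variables".

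**Timing.** The antigen-specific IgE sentence does not say which sample defines positivity. The schedule (Protocol Table 2, SAP Appendix 3) has this assay at baseline, Week 16, Week 28 and early termination, and SAP 6.4 Table 4 gives it post-baseline windows.

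**The concern.** Protocol 2.3 lists among the part B objectives to study "why some patients respond better than others (safety and/or efficacy"). That needs a comparison of the marker's association with response between the arms. A marker that predicts benefit from dupilumab has a stronger association with response on dupilumab than on placebo. A prognostic marker has a similar association in both. A CMH of positivity by response over both arms, with no treatment term, returns one number that is consistent with either.

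The undefined sampling time is a second gap. If treatment changes positivity and a post-treatment sample defines it, positivity becomes partly a proxy for arm, and the treatment effect enters the ratio systematically.

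What is at stake is the reading of one exploratory table: a ratio above 1 could be reported as identifying children who respond to dupilumab when it shows no such thing.

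**Working it through.** **Inputs from the documents** (SAP 2.3): 80 per arm; IGA 0/1 32.8% v 11.4%; EASI-75 69.7% v 26.8% (dupilumab v placebo).

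**Assumed, because the documents give no figure:** positivity prevalence 50% to 90%, size of any between-arm imbalance, and size of any marker effect.

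**The plan's own figure.** The documents state no figure for this analysis. The power statement that supplies the rates reproduces: two-sided Fisher exact power at 80 per arm is 88.9% for IGA 0/1 (stated 88%) and 99.98% for EASI-75 (stated 99%).

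**Formula.** With positivity q_D and q_P in equal arms and response p in each cell, the pooled ratio is

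RR = [(q_D·p_D+ + q_P·p_P+)/(q_D + q_P)] ÷ [((1−q_D)·p_D− + (1−q_P)·p_P−)/(2 − q_D − q_P)]

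**1. Predictive v prognostic (IGA 0/1, 50% positive in both arms).**
- Predictive only, ratio 2 on dupilumab and 1 on placebo. Negatives on dupilumab: 0.328/1.5 = 0.219; positives 0.437. Pooled: [(0.437 + 0.114)/2] ÷ [(0.219 + 0.114)/2] = 0.276/0.166 = 1.66.
- Prognostic only, ratio 1.66 in both arms: dupilumab 0.409 v 0.247, placebo 0.142 v 0.086. Pooled: 0.276/0.166 = 1.66.
- EASI-75 in the same way: 1.63 in both cases.
- With treatment added as a CMH stratum, the Mantel-Haenszel ratios stay at 1.66 and 1.63, because the arms are balanced and a common ratio is still an average.
- At 80% positivity the dupilumab-only ratio of 2 pools to 1.62 (IGA 0/1) and 1.59 (EASI-75).

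**2. No marker effect, baseline positivity.** With equal positivity the pooled ratio is 1.00. In 40,000 simulated trials (EASI-75 rates, 80% positive, randomization strata ignored) the median ratio was 1.0. The test rejected in 5.1% of trials without a treatment stratum and 4.9% with one.

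A chance imbalance moves the estimate in a given trial. With 85% v 75% positive, IGA 0/1 gives
(0.85×0.328 + 0.75×0.114)/1.6 = 0.228 and (0.15×0.328 + 0.25×0.114)/0.4 = 0.194, ratio 1.17.
EASI-75 gives 0.496/0.429 = 1.16. The SD of the imbalance is √(2×0.8×0.2/80) = 6.3 points, so 10 points is about 1.6 SD. Over 50% to 90% prevalence a 10-point imbalance gives 1.10 to 1.36 (IGA 0/1) and 1.09 to 1.32 (EASI-75). The reverse imbalance pushes the ratio below 1. Stratifying by arm returns 1.00 throughout.

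**3. No marker effect within arm, post-treatment positivity.** Suppose 80% positive on placebo and 60% on dupilumab. IGA 0/1: (0.6×0.328 + 0.8×0.114)/1.4 = 0.206; (0.4×0.328 + 0.2×0.114)/0.6 = 0.257; ratio 0.80. For 70% down to 50% on dupilumab the range is 0.88 to 0.74 (IGA 0/1) and 0.89 to 0.75 (EASI-75). This shift does not average out over repeated trials.

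**4. Precision of by-arm ratios.** At 80% positivity there are 80×0.2 = 16 negatives per arm (40 at 50%, 8 at 90%). With no marker effect, expected IGA 0/1 responders on placebo are 64×0.114 = 7.3 and 16×0.114 = 1.8. The SE of the log ratio is √(1/7.3 − 1/64 + 1/1.8 − 1/16) ≈ 0.78, so the 95% interval runs from about the estimate ÷4.6 to ×4.6. On dupilumab (21.0 and 5.2 responders) the SE is about 0.40 and the factor about 2.2. With so few events these are rough.

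**The case against.** **Pooling is inferred.** SAP 5.11 does not say in words that the arms are combined, and the opening of SAP Section 5 states a general rule of summarising by treatment group. That rule sits with the descriptive statistics. It adds no by-arm analysis to a test specified on the FAS with named strata and a single ratio. If by-arm runs were meant, the sentence should say so.

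**Randomization protects the pooled test.** A reader might infer that leaving treatment out makes the ratio a mixture of treatment and marker effects. For baseline positivity the documents do not support that reading. Allocation is 1:1 and randomized, so positivity is independent of arm in expectation. Step 2 shows a null ratio centred on 1 and a test that keeps its size. The 1.17 and 1.16 figures are chance deviations of ordinary size. This part of the objection stands.

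**The question may be association only.** SAP 5.11 speaks of association, and SAP 1.2 does not repeat the protocol's objective on differential response. The TARC and IgE models and the tape-stripping sub-study (Protocol 6.2.7.2) also serve that objective. This is fair: the limitation applies to this one analysis.

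**The alternative may be uninformative.** Step 4 bears this out at high positivity, and SAP 5.6.1 has already merged a two-patient stratum. Imprecision is a reason to show intervals. It does not give the pooled ratio a predictive meaning.

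**Little depends on it.** The analysis is optional, unadjusted for multiplicity, and absent from the testing hierarchy (SAP 5.6.3) and the list of analyses (SAP Appendix 2). That stands and sets the priority.

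**Conclusion.** The point holds in a limited form. As specified, the ratio is an arm-averaged association that cannot distinguish a predictive from a prognostic marker: at planning rates and 50% positivity, both yield 1.66 for IGA 0/1 and 1.63 for EASI-75. Systematic distortion arises only if a post-treatment sample defines positivity and treatment alters it. The SAP leaves the sample open, and under the assumed shifts the ratio falls to between 0.74 and 0.89 with no association within either arm.

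These sizes rest on the planning response rates and on assumed prevalences and effects, since the documents give none for antigen-specific IgE. No confirmatory conclusion is affected. Priority: low.

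**What to change.** In SAP 5.11, state that positivity is the baseline value, then do one of the following:

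- use the logistic model already written for TARC and IgE, with baseline positivity as a yes/no term plus treatment and their interaction; or
- add treatment as a CMH stratum and report the risk ratio within each arm with confidence intervals.

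A treatment stratum alone is not enough. It removes the effect of chance imbalance but still returns one common ratio.

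The cost is one amended sentence and one more variable in the program. The drawback is imprecision when few children are IgE-negative, so the number of negatives per arm should be shown beside the estimates, and the logistic interaction may be unstable.
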